### **12.2.3 Safety Laboratory Values and Vital Sign Measurements**

Changes from Baseline in safety laboratory values and vital sign measurements will be summarized with descriptive statistics for each treatment group at all applicable study visits.

Shift tables will be presented for changes in safety laboratory values to summarize laboratory test results collected at Baseline and Weeks 4 and 8. Normal ranges established by the central laboratory will be used to determine the shifts. A listing of all out-of-range laboratory test results at any assessment time point will also be provided. Determination of clinical significance for all out-of-range laboratory values will be made by each investigator and included in the listing. In addition, a listing of all clinically significant laboratory test results will be provided.

### **12.3 Subject Disposition**

A tabulation of subject disposition will be provided. The tabulation will include the numbers of subjects who enter the study, complete the study, and discontinue the study. The reasons for discontinuation will be included.

### **12.4 Demographics and Baseline Characteristics**

Subject demographic data and Baseline characteristics will be summarized by treatment group using descriptive statistics for the ITT, PP, and safety analysis sets. Comparisons between treatment groups will be performed to ensure comparable results.

### **12.5 Protocol Deviations**

All protocol deviations will be reported to the sponsor and recorded throughout the study. A tabulation of protocol deviations will be included in the final study report.

## **12.6 Compliance**

No formal evaluations of compliance are planned.

## **12.7 Interim Analyses**

No interim analyses are planned.

## **12.8 Additional Statistical Considerations**

### **12.8.1 Analysis Populations**

Approximately 210 adult subjects with moderate or severe psoriasis (defined as an IGA score of 3 or 4) will be enrolled and randomized in the study. With a 2:1 randomization ratio, it is anticipated that:

- Approximately 140 subjects will be randomized to receive IDP-122 (HP 0.01%) Lotion
- Approximately 70 subjects will be randomized to receive IDP-122 Vehicle Lotion

Efficacy analyses will be performed using the intent-to-treat (ITT) population and the per protocol (PP) population. The ITT analysis set will be considered primary for the evaluation of efficacy. Safety analyses will be performed using the safety population.

All subjects who are randomized and dispensed study drug will be included in the ITT analysis set.

All subjects who are randomized, receive at least 1 confirmed dose of study drug and have at least 1 post-baseline safety assessment will be included in the safety analysis set.

All subjects in the ITT analysis set who complete the Week 8 visit without any major protocol violations will be included in the PP analysis set. The PP population will include subjects in the ITT population who did not meet any of the following criteria:

- Violated the inclusion/exclusion criteria
- Used an interfering concomitant medication
- Did not attend the Week 8 visit
- Missed more than 1 post-baseline study visit prior to Week 8
- Have not been compliant with the dosing regimen (i.e., subjects must apply 80%-120% of the expected applications of study medication during participation in the study)
- Out of visit window at the Week 8 visit by more than  $\pm$  5 days

Subjects that discontinue from the study due to an adverse event related to study treatment or documented lack of treatment effect will be included in the PP population. Prior to breaking the blind, other additional criteria may be added to the list to accommodate for unforeseen events that occurred during the conduct of the trial that result in noteworthy study protocol violations.

The number of subjects in each analysis set will be summarized. Reasons for study withdrawal during the blinded study will be summarized using frequencies and percentages by treatment group.

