**Statistical methods:**

All subjects who are randomized and dispensed study drug will be included in the intent-to-treat (ITT) analysis set. All subjects in the ITT analysis set who complete the Week 8 visit without any major protocol violations will be included in the per protocol (PP) analysis set. All subjects who are randomized, receive at least 1 confirmed dose of study drug, and have at least 1 post-baseline assessment will be included in the safety analysis set.

The ITT analysis set will be considered primary for the evaluation of efficacy. The primary method of handling missing efficacy data will be the method of Markov Chain Monte Carlo (MCMC) multiple imputation; no imputations will be made for missing safety data.

*Efficacy:*Efficacy Endpoints

The efficacy endpoints are intended to compare once daily application of IDP-122 Lotion and vehicle. Specifically, the efficacy endpoints include:

- The percent of subjects with treatment success, defined as at least a 2 grade improvement from Baseline in the IGA score and an IGA score equating to “clear” or “almost clear” at Weeks 2, 4, 6, 8 and Week 12 (4-week follow-up), as summarized using descriptive statistics.
- The percent of subjects with at least a 2-grade improvement from Baseline in the score for each of the signs of psoriasis (erythema, plaque elevation, and scaling) at Weeks 2, 4, 6, 8 and Week 12 (4 week FU), as summarized using descriptive statistics for the target lesion treated with study drug.

Inferential Statistics**Primary Efficacy**

The primary efficacy endpoint will be the percent of subjects with treatment success, defined as at least a 2-grade improvement from Baseline in IGA score and an IGA score equating to “Clear” or “Almost Clear”. The primary efficacy endpoint will be used to compare once daily application of IDP-122 Lotion with its vehicle. The percent of subjects with treatment success at Week 8 will be analyzed using Cochran-Mantel-Haenszel (CMH) tests stratified by analysis center.

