13. The investigator/evaluator will assess the signs of psoriasis (erythema, plaque elevation, and scaling) of the selected target lesion.
14. The investigator/evaluator will evaluate local skin reactions (itching, dryness, burning/stinging, skin atrophy, striae, telangiectasia and folliculitis) by observation and questioning the subjects as necessary.
15. Randomize the subject using the IRT system and record the assigned kit number in the source document and in the eCRF.
16. The study coordinator or designee will weigh each tube within the assigned kit and dispense them to the subject. A study diary calendar will also be dispensed.
17. The study coordinator or designee will instruct the subject on the proper application procedure for the study drug. For the first application, the subject will apply the study drug at the investigational center during the day under the direction of the study coordinator or designee. The study drug should be applied after all clinical assessments. The subjects will be asked to avoid exposure to direct sunlight and artificial ultraviolet light sources on the initial application day and thereafter. The study coordinator or designee will instruct the subjects to apply the study drug once daily at home.
18. Record any AEs reported spontaneously by the subject.
19. Schedule the next study visit at Week 2 (Day 14 ± 3 days).

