**Note:** For subjects who exit the study prior to completing Week 8, perform all of the assessments scheduled for Week 8 at the time that the subject discontinues or within 2 weeks of subject discontinuation. The subject will be asked to come back for the 4-week post-treatment cessation follow-up visit.

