## **12.2 Assessment of Safety**

### **12.2.1 Adverse Events**

The primary analysis of safety will be conducted at Week 8. There will be a tabulation, however, of the AE's that start in the period post the Week 8 to Week 12 visit. All AEs occurring during the study will be recorded and classified using terminology from the Medical Dictionary for Regulatory Activities (MedDRA). All reported treatment-emergent adverse events (TEAEs), defined as any AE with an onset on or after the date of first study drug application, will be summarized by treatment group and will provide the number of subjects reporting TEAEs, system organ class, preferred term, severity, and relationship to study drug. When summarizing TEAEs by severity or relationship to study drug, each subject will be counted only once within a system organ class or a preferred term using the event with the greatest severity or causality, respectively, within each category. All reported SAEs will be summarized by the number of subjects reporting the event, system organ class, preferred term, severity, and relationship to study drug.

All information pertaining to AEs noted during the study will be listed by treatment group and subject and will include a verbatim description of the event as reported by the investigator, as well as the preferred term, system organ class, start date, stop date (if stopped), seriousness, severity, action taken regarding the study drug, corrective treatment, outcome, and relationship to the study drug. In addition, a listing of subjects who prematurely discontinue from the study due to AEs will be provided as well as a listing of subjects who reported an SAE.

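### A treated subject who is never assessed again is left out of the adverse event tables, even if a treatment-emergent event was recorded

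*Combined protocol and SAP*

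**What the plan says.** Section 12.8.1 (Analysis Populations) puts in the safety set those randomized subjects who "receive at least 1 confirmed dose of study drug and have at least 1 post-baseline safety assessment", and adds: "Safety analyses will be performed using the safety population". The Synopsis (Statistical methods) asks instead that they "receive at least 1 confirmed dose of study drug, and have at least 1 post-baseline assessment", so there the later assessment need not be a safety one. Neither place says what counts as such an assessment.

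The surrounding text matters:

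- **First dose.** Section 11.1.2, step 17, has it that "the subject will apply the study drug at the investigational center during the day under the direction of the study coordinator or designee". The next listed step is: "Record any AEs reported spontaneously by the subject".
- **Treatment-emergent AE (TEAE).** Section 12.2.1 has it "defined as any AE with an onset on or after the date of first study drug application". No later visit is needed. The same section says that all reported TEAEs and serious AEs (SAEs) are summarized and that AE information is listed by subject.
- **Early exit.** For subjects who leave before Week 8, the note in Section 11.1.4 tells sites to "perform all of the assessments scheduled for Week 8 at the time that the subject discontinues or within 2 weeks of subject discontinuation", and the subject is asked back for follow-up. The Synopsis (Methodology) has subjects who discontinue because of AEs return for the 4-week follow-up visit.
- **Non-return.** Section 8.3 foresees loss to follow-up. Section 12 rules out imputing missing safety data.

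**The concern.** Membership of the safety set depends on something that happens after treatment starts, namely being assessed again, and not on exposure alone. The usual use of a second condition is to guard against doubtful exposure. Here that purpose is already served, because the first dose is supervised in clinic. What the condition does is take out people known to have been treated who have no later safety record.

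This produces a conflict inside the plan. A Day 0 reaction can meet the TEAE definition and be on file, yet not be tabulated, although Section 12.2.1 undertakes to summarize all reported events. The same holds for an event that becomes known by telephone or spontaneous report, if that contact is not an assessment. The stake is the numerator and denominator of the AE and SAE tables. For uncommon events, a few subjects decide whether the table shows zero.

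**Working it through.** **Plan figure.** The documents give no figure for the size of the safety set or for non-return. Their one design figure, power above 95% with 140 and 70 subjects, reproduces at 98.0% (exact enumeration of Fisher's test, 33.3% against 9.7%, two-sided 0.05). It does not depend on this point, because efficacy uses the ITT set.

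**Who is excluded.** Take a subject who applies the first dose in clinic, has a reaction noted before leaving, and never returns.

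1. Confirmed dose: yes (Section 11.1.2, step 17).
2. AE recorded: yes (step 18; Section 11.5.2 takes queried, observed and spontaneous reports).
3. TEAE: yes, since onset is on the date of first application (Section 12.2.1).
4. Post-baseline safety assessment: none, unless the record made at the Baseline visit counts, which is not stated.
5. In the safety set: no. In the tables as Section 12.8.1 defines them: no. In the summaries as Section 12.2.1 describes them: yes.

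If the same subject returns once for a termination or follow-up visit, step 4 is met and the subject is in.

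**Size per subject.** Inputs: about 140 IDP-122 and 70 vehicle subjects (Section 12.8.1). One subject is 1/140 = 0.71% or 1/70 = 1.43%. Suppose *k* treated IDP-122 subjects have a recorded event and are excluded, and *x* others with the event are retained. The rate is (*x* + *k*)/140 on all treated subjects and *x*/(140 − *k*) as tabulated. The values of *k* and *x* are assumptions.

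| k | x = 0: all treated | x = 0: tabulated | x = 3: all treated | x = 3: tabulated |
|---|---|---|---|---|
| 1 | 0.71% | 0.00% | 2.86% | 2.16% |
| 2 | 1.43% | 0.00% | 3.57% | 2.17% |
| 3 | 2.14% | 0.00% | 4.29% | 2.19% |
| 5 | 3.57% | 0.00% | 5.71% | 2.22% |

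**How often anyone is excluded.** Assume a share *d* of treated subjects with no later assessment, whether or not they had an event. Expected exclusions are 140*d* and 70*d*. The chance of at least one in 210 is 1 − (1 − *d*)^210.

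| d | IDP-122 | Vehicle | Chance of at least one |
|---|---|---|---|
| 0.5% | 0.7 | 0.35 | 65% |
| 1% | 1.4 | 0.7 | 88% |
| 2% | 2.8 | 1.4 | 99% |
| 5% | 7.0 | 3.5 | >99.9% |

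**Effect of an exposure-only set.** Assume 3 or 7 of 140 never return and 5% of the rest have an AE, so that 5.0% is tabulated now.

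- If all non-returners had a *recorded* AE: (137 × 0.05 + 3)/140 = 7.0%, or (133 × 0.05 + 7)/140 = 9.8%.
- If none of them has a recorded AE: (137 × 0.05)/140 = 4.9%, or (133 × 0.05)/140 = 4.75%.

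The change can therefore move a rate either way, depending on what was recorded before contact was lost.

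**The case against.** A reader might infer that anyone who stops right after the first application leaves the AE tables. The documents do not support that. Early stoppers are to have the full set of Week 8 assessments at discontinuation or within 2 weeks and are asked back for follow-up, and the Synopsis is firmer about return for AE discontinuations than for other early exits. One such visit keeps the subject in.

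A reader might also infer that the rule must make the active arm look cleaner. That is not shown. Nothing in the documents says that non-returners are mostly people with reactions, or that non-return differs by arm. The 7.0% to 9.8% scenario needs a non-return share, a background rate and a recorded reaction in every non-returner, none of which is documented.

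Nor do recorded events vanish from the report. Section 12.2.1 asks for listings of AE information, AE discontinuations and SAE subjects without naming an analysis set, and Section 11.5.6 requires SAEs that the investigator learns of within 30 days of stopping to be reported. The gap between Synopsis and body is narrow in practice, because AEs and local skin reactions are scheduled at every post-baseline visit. Section 12 also defers detail to a separate SAP. The text available here contains no SAP definition of the term, but one could settle it.

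All of this narrows the point. It does not remove it. The termination and follow-up visits depend on the subject coming back, the Week 8 assessments before other therapy are sought only where possible, and Section 8.3 expects some loss to follow-up. A listing does not correct a tabulated rate, and Sections 12.2.1 and 12.8.1 still disagree.

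**Conclusion.** The point holds for one group: treated subjects with no safety assessment after Baseline. They are outside the set used for the AE tables even when a TEAE is on file, and this contradicts the undertaking to summarize all reported events. Exposure is already confirmed on Day 0, so the extra condition gains nothing.

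The effect is about 0.7 percentage points per excluded IDP-122 subject with a recorded event (1.4 points in the vehicle arm), and probably concerns few subjects. That expectation is a judgement, since the documents give no rate. The direction of bias is plausible, because an early reaction is one reason not to return, but it is not certain. The conclusion assumes that an AE noted at the Baseline visit or by telephone is not a post-baseline safety assessment. If it is, those subjects are already in the set and only the wording needs repair. No efficacy result is affected.

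**What to change.** In Section 12.8.1 and in the Synopsis, define the safety set as every randomized subject with one or more confirmed applications of study drug, and delete the requirement for a later assessment. Leave by-visit summaries (local skin reactions, laboratory values, vital signs) on subjects with data at that visit. Name the safety set in Section 12.2.1 so that the AE summaries and the population definition agree.

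The cost is one sentence in two places plus that alignment, with no new data. The downside is that treated subjects with no follow-up data enter the denominator as non-events and slightly dilute the rates, as the 4.9% and 4.75% figures show. Report their number by arm so that a reader can judge this.

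If the present definition is kept, the least that is needed is one wording in both places and a statement on whether AEs recorded after the Day 0 application, or reported by telephone, count as a post-baseline safety assessment.

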### 12.8.2 Sample Size Determination

The following power calculations were computed using the observed Week 8 dichotomized IGA efficacy data in the ITT population from the Phase 2 study V01-118A-201. SAS PROC POWER with the Fisher's exact test option was used to calculate the power for various sample sizes using a two-sided test with an alpha of 0.05. Table 5 presents the efficacy estimates derived from study V01-118A-201.

**Table 5. Percent Dichotomized IGA Success for Treatment Groups**

	IDP-122* (IDP-118 Monad (HP 0.01%) Lotion)	IDP-122 (IDP-118) ** Vehicle
Percent Success	33.3%	9.7%

Success was defined as at least a 2-grade improvement from Baseline in the IGA score and an IGA score equating to "Clear" or "Almost Clear".

\*IDP-122 refers to the (IDP-118 Monad (HP 0.01%) Lotion) used in the V01-118A-201 Study

\*\*IDP 118 Vehicle composition used in the V01-118A-201 is equivalent to the vehicle that will be used in this study (IDP 122 Vehicle Lotion).

One hundred forty (140) IDP-122 treated subjects and seventy (70) vehicle treated subjects will have greater than 95% power to detect a statistically significant outcome for a two-sided test with an alpha level of 0.05.

It was noted that the estimates extracted from the above studies are based on the LOCF method of handling missing values while the proposed Phase 3 analysis will account for missing values using multiple imputations. The power stated above sufficiently exceeds 95% which will compensate for the difference in handling of missing data.

### **12.8.3 Handling of Missing Data**

The method of multiple imputation will be used (see [Section 12.1.4](#)).

### **12.8.4 Multicenter Issues**

The study will be conducted at multiple investigational centers in North America with the intention of pooling the results for analysis.

### **12.8.5 Multiplicity Issues**

Not applicable.

### **12.8.6 Windowing Rules**

The timing of all study visits is relative to Baseline (Day 0). The Week 2 and 4 visits should occur within  $\pm$  3 days of the scheduled times, the Week 8 visit should occur within  $\pm$  5 days of the scheduled time, and Week 12 visits should occur within  $\pm$  7 days of the scheduled times.

## **13 Quality Control and Quality Assurance**

### **13.1 Study Monitoring**

An Investigator Meeting or an initiation visit will be conducted with the principal investigator and study coordinators by sponsor and/or its designee. During this meeting, an extensive review and discussion of the protocol, the role of the study technician, all study procedures, source documents, and eCRFs will be conducted. Evaluation scales will be reviewed extensively and documentation of training will be recorded for training of sponsor-approved evaluators.

The study monitors/clinical research associates will be trained prior to study initiation. Following this training, an overview of the study disease and study material background will be understood. Specific monitoring guidelines and procedures to be followed during monitoring visits will also be utilized. During the course of the study, all data will be 100% source document verified by the monitors. All subject source records must be made available to the monitors.

The conduct of the study will be closely monitored by the sponsor following GCP guidelines. The reports of these verifications will also be archived with the study report. In addition, inspections or on site audits may be carried out by local authorities or by the sponsor's Quality Assurance Department. The investigators will allow the sponsor's representatives and any regulatory agency to examine all study records, corresponding subject medical records, clinical dispensing records and storage area, and any other documents considered source documentation. The investigators agree to assist the representative, if required.

### **13.2 Audits and Inspections**

The study will be conducted under the sponsorship of Valeant in conformation with all appropriate local and federal regulations, as well as ICH guidelines. Interim and end of study audits of raw data, study files, and final report may be conducted by Valeant's Quality Assurance Department or designee.

The sponsor is responsible for implementing and maintaining quality assurance and quality control systems to ensure that studies are conducted and data are generated, documented, and reported in compliance with the protocol, GCP, and applicable regulatory requirements. In addition, the sponsor will be responsible for securing agreement from all involved parties to ensure direct access to all study related investigational centers, source data/documents, eCRFs, and reports for the purpose of monitoring and auditing by the sponsor, and inspection by domestic and foreign regulatory authorities.

### **13.3 Data Quality Assurance**

All assessments performed will be accurately documented in the subject's source documents and eCRFs. The investigator or designee will enter the information required by the protocol into the source documents and eCRFs provided by the sponsor or designee. Subjects will be identified in the eCRFs by their assigned subject number and initials only.

The investigators must read the protocol thoroughly and must follow the instructions exactly. Any deviations should be agreed to by prior discussion between the sponsor and the investigator, with appropriate written protocol amendments made prior to implementing the agreed changes. Any amendment containing major modifications (particularly if it may involve an increased risk to the subjects) will be approved by the IRB before it may be implemented. No change in the conduct of the study can be instituted without written approval from the sponsor.

